#### **10.2.3.32 Month 15 + 3 days ( $\pm 1$ day)**

- Telephone call to subject to ensure there are no signs or symptoms of retinal detachment or endophthalmitis.

#### **10.2.3.33 Month 16 ( $\pm 7$ days)**

##### **Pre-Injection**

- Protocol refraction and visual acuity (4 meters) using ETDRS chart (SE)
- Low Luminance ETDRS Visual Acuity (SE)
- Tonometry and Ophthalmologic examination (SE)
- Randomized Treatment: Zimura™/Sham

##### **Post-injection**

- Ophthalmologic Examination - at least 30 minutes after the last (whether first or second) injection (SE)
- Tonometry (SE):
  - If one injection is administered (including sham):
    - The IOP should be recorded at least 30 minutes after the injection.
  - If two injections are administered (including sham):
    - The second injection may NOT be administered until the IOP is  $\leq 21$  mm Hg or within 5 mm Hg of the baseline IOP on the day of injection, at which time the IOP will be recorded.
    - The IOP should be recorded at least 30 minutes after the 2nd injection.

#### **10.2.3.34 Month 16 + 3 days ( $\pm 1$ day)**

- Telephone call to subject to ensure there are no signs or symptoms of retinal detachment or endophthalmitis.

#### **10.2.3.35 Month 17 ( $\pm 7$ days)**

##### **Pre-Injection**

- Protocol refraction and visual acuity (4 meters) using ETDRS chart (SE)
- Low Luminance ETDRS Visual Acuity (SE)
- Tonometry and Ophthalmologic examination (SE)
- Randomized Treatment: Zimura™/Sham

### **Post-injection**

- Ophthalmologic Examination - at least 30 minutes after the last (whether first or second) injection (SE)
- Tonometry (SE):
  - If one injection is administered (including sham):
    - The IOP should be recorded at least 30 minutes after the injection.
  - If two injections are administered (including sham):
    - The second injection may NOT be administered until the IOP is  $\leq 21$  mm Hg or within 5 mm Hg of the baseline IOP on the day of injection, at which time the IOP will be recorded.
    - The IOP should be recorded at least 30 minutes after the 2nd injection.

#### **10.2.3.36 Month 17 + 3 Days ( $\pm 1$ day)**

- Telephone call to subject to ensure there are no signs or symptoms of retinal detachment or endophthalmitis.

#### **10.2.3.37 Month 18 ( $\pm 7$ days)**

- [REDACTED]
- Protocol refraction and visual acuity (4 meters) using ETDRS chart (OU)
- [REDACTED]
- Low Luminance ETDRS Visual Acuity (OU)
- Goldmann Applanation Tonometry and Ophthalmologic examination (OU)
- Vital Signs
- 12-Lead ECG
- Color fundus photographs (OU)
- Fluorescein Angiograms (OU, transit study eye)
- Optical Coherence Tomography (OU)
- Fundus Autofluorescence (OU)
- Laboratory Tests
- Serum pregnancy test (if applicable)

### **10.2.3.38 Early Withdrawal**

- [REDACTED]
- Protocol refraction and visual acuity (4 meters) using ETDRS chart (OU)
- [REDACTED]
- Low Luminance ETDRS Visual Acuity (OU)
- Goldmann Applanation Tonometry and Ophthalmologic examination (OU)
- Vital Signs
- 12-Lead ECG
- Color fundus photographs (OU)
- Fluorescein Angiograms (OU, transit study eye)
- Optical Coherence Tomography (OU)
- Fundus Autofluorescence (OU)
- Laboratory Tests
- Serum pregnancy test (if applicable)

Adverse events are recorded up until 30 days after the last dose of study drug or until the last follow up visit of the trial, whichever comes later. An adverse event that is ongoing at the last follow-up study visit is required to be followed up until the event resolves or stabilizes at a level acceptable to the Investigator and/or Sponsor. If the subject still presents with any treatment-related toxicity, the follow-up period will be extended until return to baseline status or until the condition has stabilized.

### **10.3 Withdrawal from Trial**

Subjects have the right to withdraw from the trial at any time for any reason. The Investigator (after consultation with the Sponsor) or Sponsor also have the right to withdraw subjects from the trial in the event of concurrent illness, adverse events, treatment-failure after a prescribed procedure, protocol violations, cure, administrative or other reasons.

Final trial assessments as outlined in the Study Assessments Chart, Section 3, should be performed on all subjects who withdraw. Subjects who withdraw due to an adverse event should be followed until resolution of the adverse event, or an adequate explanation for the event is obtained.

Subjects who withdraw for any reason should have assessments performed according to the Early Withdrawal schedule.

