## 10.4 Trial Discontinuation

The reason for a subject discontinuing from the trial will be recorded in the source documentation and case report form. A discontinuation occurs when an enrolled subject ceases participation in the trial, regardless of the circumstances, prior to completion of the protocol. The investigator must determine the primary reason for discontinuation. A discontinuation must be reported immediately to the clinical monitor or his/her designated representative if it is due to a serious adverse event (SAE) (see Section 12.3). The final evaluation required by the protocol will be performed at the time of trial discontinuation. The investigator will record the reason for trial discontinuation, provide or arrange for appropriate follow-up (if required) for such subjects, and document the course of the subject's condition.

Premature termination of this clinical trial may occur because of a regulatory authority decision, change in opinion of the IRB/EC, drug safety problems, or at the discretion of Ophthotech Corp.

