### **11.6.4 Efficacy Analysis**

The efficacy analysis will be conducted on all randomized and treated subjects according to the intention-to-treat principle.

For normal endpoints, treatment groups will be compared through an analysis of variance including stratification factors.

For binary endpoints, treatment groups will be compared through Mantel-Haenszel or Cochran-Mantel-Haenszel  $\chi^2$  tests adjusting for strata as above.

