### 3.4.3 Handling Missing Data in Efficacy analyses

Methods that take into account the presence of missing data and that yield valid estimates under the assumption of data missing at random (MAR) will be used. In particular, a Model for Repeated Measures fitted by Restricted Maximum Likelihood method will be used in the primary analysis, where as-observed data will be used with no imputation. Multiple-imputation will be used in sensitivity analyses, whenever necessary, to impute the missing data, as described in Section 7.6.1.

Of note, the proper approach to address missingness is the prevention of missing data. The sponsor will implement aggressive proactive approaches to minimize the number of patients who are not assessed at 12 months.

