### 4 STUDY SUBJECTS

### 4.1 **DISPOSITION OF SUBJECTS**

The number of subjects randomized and treated, by treatment arm will be presented. The reason for exclusion from one or more analysis sets will be summarized.

The frequency of premature discontinuations from the study treatment prior to Month 12 will be given by treatment arm and overall. The details of the 'Non-fatal Adverse Event', 'Protocol violation', 'Investigator decision', 'Sponsor Decision', 'Subject request', 'Lost to Follow-Up', 'Subject Non-Compliance', 'Death', or 'Other' will be included in a listing.

The frequency of premature discontinuations from the study prior to Month 12 will be given for the ITT and PP populations by treatment arm and overall. The primary reason for non-completion of the study will be summarized.

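### Subjects withdrawn by the investigator or sponsor are scheduled only an Early Withdrawal evaluation, so Month 6 or Month 12 FAF that could still be obtained is lost

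*Protocol*

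**What the plan says.** Protocol 10.3 gives the investigator (after consulting the sponsor) or the sponsor the "right to withdraw subjects from the trial in the event of concurrent illness, adverse events, treatment-failure after a prescribed procedure, protocol violations, cure", and for administrative or other reasons. The right concerns the trial, not only the injections. The same section adds: "Subjects who withdraw for any reason should have assessments performed according to the Early Withdrawal schedule". Protocol 10.4 fixes the timing: "The final evaluation required by the protocol will be performed at the time of trial discontinuation".

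After that visit two things may follow. Under 10.3, a subject withdrawn for an adverse event stays under observation until that event resolves or is explained. Under 10.4 the investigator will "provide or arrange for appropriate follow-up (if required) for such subjects, and document the course of the subject's condition". Neither names a later FAF.

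The Early Withdrawal visit (10.2.3.38) does include FAF in both eyes. SAP 3.4.2 lets that image stand in for a missing scheduled visit only if it falls within that visit's window; otherwise the visit is missing. SAP 3.2.1 requires Baseline and at least one post-Baseline GA value for the primary analysis.

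Against this stand Protocol 11.6.4, "The efficacy analysis will be conducted on all randomized and treated subjects according to the intention-to-treat principle", and SAP 3.4.3, "The sponsor will implement aggressive proactive approaches to minimize the number of patients who are not assessed at 12 months". SAP 4.1 reports the two kinds of stopping separately. For treatment, "The frequency of premature discontinuations from the study treatment prior to Month 12 will be given by treatment arm and overall"; a parallel sentence covers leaving the study.

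**The concern.** Some withdrawn subjects could still be imaged at Month 6 or Month 12, but once withdrawn they have no visit at which to be imaged. The plan's own rule then creates the missing primary-endpoint data. The grounds include protocol violations. SAP 4.3 excludes subjects with significant violations only from the Per-Protocol set and still summarises them for ITT, so it expects them to stay in the ITT data. The grounds also include adverse events and treatment failure, which the primary model does not contain: its terms are treatment, visit, part and the stratification factors (SAP 7.2). Missing-at-random is least secure for such withdrawals.

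The repeated-measures model uses observed data without imputation. It in effect fills a withdrawn Zimura subject's Month 12 value from same-arm subjects who were imaged then, most of them still receiving injections. If growth returns toward the Sham rate after stopping, the estimate exceeds the reduction that would be seen with everyone followed. Decisions are guided by the 14% and 24.5% cut-offs, and the planning effect of 28% lies only 3.5 points above the upper one.

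**Working it through.** **1. The plan's own figures.** Protocol 11.3 gives cut-offs of 14% and 24.5%, with chances of 10% and 1.25% of reaching them under no effect. The implied SE of the estimated reduction is 24.5 / z(0.9875) = 24.5 / 2.241 = 10.93 points, or 14 / z(0.90) = 14 / 1.282 = 10.92 points. The two agree. At a true 28%:

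- P(estimate ≥ 24.5%) = Φ((28 − 24.5) / 10.93) = 62.6%; the plan states 63%.
- P(estimate ≥ 14%) = Φ((28 − 14) / 10.93) = 90.0%; the plan states 90%.

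The information is 80×80/160 = 40 for 4 mg and 26×26/52 + 40×80/120 = 39.67 for 2 mg, so one SE serves both. This shows internal consistency only, because the SE comes from the plan's cut-offs. These figures use all randomized subjects, with no stated allowance for dropout.

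**2. Gap for withdrawn subjects.** The inputs are assumptions except the 28%: a fraction d of the Zimura arm is withdrawn, the effect is 28% on drug, and there is none after stopping, which occupies a fraction f of the year.

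- Reduction with everyone followed = 28 × (1 − d × f).
- Target of the missing-at-random model without off-drug data ≈ 28.
- Overstatement = 28 × d × f.

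| d | Stop at | f | All-followed reduction | Overstatement (points) | In SE units | P(estimate ≥ 24.5%) at the all-followed value |
|---|---|---|---|---|---|---|
| 10% | Month 6 | 6/12 | 26.6% | 1.4 | 0.13 | 58% |
| 20% | Month 6 | 6/12 | 25.2% | 2.8 | 0.26 | 53% |
| 10% | Month 2 | 10/12 | 25.7% | 2.3 | 0.21 | 54% |
| 20% | Month 2 | 10/12 | 23.3% | 4.7 | 0.43 | 46% |

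The last column is Φ((all-followed reduction − 24.5) / 10.93), to be compared with 62.6% at 28%.

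**3. Smaller rates.** If only 2–5% were withdrawn and still imageable, stopping at Month 6, the gap would be 28 × 0.02 × 0.5 = 0.3 to 28 × 0.05 × 0.5 = 0.7 points.

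**4. No drug effect.** Replacing 28 by 0 makes the overstatement 0 for every d and f. This mechanism does not raise the 1.25% or 10% false-positive rates.

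**5. The planned Sham-mean analysis (SAP 7.6.1).** Giving withdrawn Zimura subjects the Sham mean yields 28 × (1 − d): 25.2% at d = 10% and 22.4% at d = 20%. Each is below the corresponding all-followed values in the table, so on these assumptions the primary and Sham-mean results bracket the answer. They do not locate it.

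**The case against.** Two stronger readings are tempting, and the documents support neither.

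A reader might infer that the ITT comparison becomes an on-treatment one. It does not. SAP 3.2.1 analyses subjects as randomized whatever dose they received, and withdrawal is a discretionary right, not an automatic result of stopping injections. The shift concerns withdrawn subjects only.

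A reader might also infer that nobody can stop injections and stay in the trial. The documents treat these as separate events. Protocol 11.6.6 counts subjects whose medication was permanently stopped, SAP 4.1 and 8.2 report treatment discontinuation in its own right, and SAP 8.2 defines the end of the first year for a subject with a Month 12 visit but no Month 12 injection. What is absent from 10.3 and 10.4 is any instruction that such subjects keep their imaging visits.

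Other points stand in part:

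- An Early Withdrawal FAF inside a window is used. How many would qualify cannot be computed, because the window widths (SAP Appendix 1) are not in the public text; neither is the assessments chart (Protocol Section 3).
- Subjects who refuse, die or are lost cannot be recovered by any wording, so d overstates what this rule causes.
- Complete and immediate loss of effect on stopping is an unfavourable assumption.
- The cut-offs are guidelines, not strict rules.
- Every Part 2 arm receives two procedures, so injection burden is a weak ground for expecting losses to differ between those arms.

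The sensitivity analyses help but do not close the gap. The shift analysis as described moves missing values toward smaller change, which for GA means less growth and is opposite to the concern, although treatment-dependent shifts are also planned. Neighbouring-case imputation borrows from observed subjects, who would include little off-treatment experience. The SAP itself warns that the mean-imputation analyses may be biased.

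**Conclusion.** The point holds in limited form. Protocol 10.3 and 10.4, read with SAP 3.4.2, can lose obtainable Month 6 or Month 12 FAF for withdrawn subjects and can remove some of them from the primary analysis. That works against Protocol 11.6.4 and SAP 3.4.3. On the stated assumptions the overstatement is about 1.4 to 4.7 points, or 0.13 to 0.43 of the implied SE. It is smaller if fewer withdrawn subjects could be imaged or if some effect persists. Only the largest scenario (20% stopping at Month 2) brings the all-followed reduction below 24.5%. The withdrawal rate is assumed throughout, because the documents give none.

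A reader might also infer that the false-positive rates are compromised. By this mechanism they are not, since the gap is zero when the drug has no effect. Severity: should-fix, because the loss is avoidable, possibly informative and cheap to prevent.

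**What to change.** Reconcile Protocol 10.3 and 10.4 with the SAP:

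- Define discontinuation of study treatment separately from withdrawal from the trial.
- Ask subjects who stop injections, for whatever reason, and who still consent and can safely attend, to keep the already scheduled Month 6 and Month 12 visits for FAF and BCVA.
- Keep the Early Withdrawal visit for those who decline or cannot attend.
- State in SAP 7.2 that these readings enter the primary ITT model whatever the treatment status, so that the target is the effect regardless of treatment discontinuation.

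The clinical grounds for stopping treatment, or for withdrawing a subject for safety, are left unchanged.

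The cost is protocol and SAP wording plus one or two existing visits for each subject who stops treatment. The estimate may become slightly less favourable because time off treatment is counted. Images already missed cannot be recovered.

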## 10.4 Trial Discontinuation

The reason for a subject discontinuing from the trial will be recorded in the source documentation and case report form. A discontinuation occurs when an enrolled subject ceases participation in the trial, regardless of the circumstances, prior to completion of the protocol. The investigator must determine the primary reason for discontinuation. A discontinuation must be reported immediately to the clinical monitor or his/her designated representative if it is due to a serious adverse event (SAE) (see Section 12.3). The final evaluation required by the protocol will be performed at the time of trial discontinuation. The investigator will record the reason for trial discontinuation, provide or arrange for appropriate follow-up (if required) for such subjects, and document the course of the subject's condition.

Premature termination of this clinical trial may occur because of a regulatory authority decision, change in opinion of the IRB/EC, drug safety problems, or at the discretion of Ophthotech Corp.

## 11 STATISTICAL METHODS

The following summarizes the statistical approaches that will be employed in this trial designed to compare the effects of 2 mg and 4 mg doses of Zimura™ against the Sham control arm, regarding geographic atrophy secondary to Dry AMD.

### 11.1 Study Design

This is a randomized, double-masked, Sham controlled [REDACTED] study that will obtain evidence regarding the effects of multiple dose levels of Zimura™ in reducing the rate of GA growth over 12 months, when compared with the Sham control.

This [REDACTED] trial will provide evidence suggesting that a dose of Zimura™:

- Is not plausibly more efficacious than the Sham control, and should be discarded in its current formulation in this indication;
- Is plausibly more efficacious than the Sham control and should be evaluated definitively in a subsequent Phase 3 clinical trial; or
- Is more efficacious than the Sham control, with strength of evidence meeting the standard requirement of a 0.0125 one-sided false-positive error rate, adjusting for the multiple comparisons of 2 mg and 4 mg doses against the Sham control. A confirmatory trial likely would be required for regulatory approval.

Eligible subjects that consent to participate will be randomized to Zimura™ or Sham control in two parts of the trial. In Part 1, approximately 77 subjects are randomized to Zimura™ 1 mg vs Zimura™ 2 mg vs Sham control, in a 1:1:1 allocation. In Part 2, approximately 200 subjects are randomized to Zimura™ 2 mg vs Zimura™ 4 mg vs Sham control, in a 1:2:2 allocation. A total of approximately 277 subjects are to be randomized.

## **11.2 Endpoints**

### **11.2.1 Primary Efficacy Endpoint**

#### Primary Efficacy Endpoint:

- Mean rate of change in GA over 12 months measured by fundus autofluorescence (FAF) at three time points: Baseline, Month 6, Month 12

#### Secondary Efficacy Endpoints:

Secondary efficacy endpoints will be assessed from Baseline to Month 12:

- Mean change in best corrected visual acuity (ETDRS letters) from Baseline to Month 12
- Mean change in low luminance best corrected visual acuity (ETDRS letters) from Baseline to Month 12

### **11.2.2 Safety and Tolerability Endpoints**

#### Safety and tolerability endpoints:

- All adverse events reported, whether or not deemed related to the injection procedure or study treatment
- All SAEs, whether or not deemed related to the injection procedure or study treatment
- Laboratory data (blood: hematology, renal function, hepatic function, and electrolytes; urinalysis)
- Ophthalmic variables (IOP, ophthalmic examination, fluorescein angiograms, FAF, and OCT)
- Vital sign measurements
- 12-lead ECG

### 11.3 Determination of Sample Size and Statistical Rationale

The sample size determination for this study is based on [REDACTED] screening methodology presented in Fleming and Richardson (2004). The power calculations are based on the recently released results from a clinical trial of a complement inhibitor, including the estimated precision of the estimated effects on rate of GA growth over 12 months, and including the plausible effect size for Zimura™.

A total of approximately 277 subjects will be enrolled. When follow-up is complete for the primary analysis based on 12-month follow-up, the data base will be locked. Information post-12 months will remain fully confidential until completion of 18-month follow-up. By pre-specification, a hierarchical analysis will be performed where the treatment effect on the rate of GA growth over 18 months will be statistically assessed if statistical significance is achieved on the rate of GA growth over 12 months.

[REDACTED] the primary analyses will be based on comparisons of Zimura™ 2 mg vs the Sham control, and Zimura™ 4 mg vs Sham control. For the comparison of Zimura™ 2 mg vs Sham control, the 26 subjects randomized to Zimura™ 2 mg and 26 subjects randomized to Sham control from Part 1 will be combined with the 40 subjects randomized to Zimura™ 2 mg and 80 subjects randomized to Sham control from Part 2, where the analysis will be stratified by Part 1 vs Part 2. The comparison of Zimura™ 4 mg vs Sham control will be based on the 80 subjects randomized to each of these two arms in Part 2.

The primary analysis [REDACTED] for each of the two pairwise comparisons of an active dose of Zimura™ vs the Sham control is formally based on a three-category decision guideline. To be specific, the decision guideline for this trial is based on whether the estimated reduction in rate of GA growth over 12 months for a dose of Zimura™ versus Sham control is less than 14%, is from 14% up to 24.5%, or is at least 24.5%.

Note that these categories should not be interpreted as providing strict decision rules but rather as guidelines that will be factored into a broader scientific assessment of the benefit to risk profile of the Zimura™ dose regimen. This broader assessment will include consideration of safety, of supportive efficacy endpoints, and of relevant information external to this trial. Specifically, the decision guidelines for this trial are:

1. If the estimated reduction in the rate of GA growth over 12 months is less than 14%, then this dose of Zimura™ is not plausibly more efficacious than the Sham control; its utility in this indication should be reconsidered.
2. If the estimated reduction in the rate of GA growth over 12 months is from 14% to up to 24.5%, then this dose of Zimura™ is plausibly more efficacious than the Sham control and should be evaluated in a subsequent Phase 3 clinical trial.

In planning the design of the confirmatory Phase 3 trials, this trial (and other information that emerges during the conduct of this trial) will provide important insights through consideration of:

- a. The estimated benefit-to-risk profile of this dose of Zimura™;
  - b. Possible refinements in the dose/schedule of Zimura™
  - c. Approaches to improve adherence to the Zimura™ regimen;
  - d. Modifications to defining eligibility criteria to enhance enrichment;
  - e. Approaches to achieving timely accrual of study participants at centers with established ability to provide high quality implementation of the trial and high quality data.
3. If the estimated reduction in the rate of GA growth over 12 months is at least 24.5%, then this dose of Zimura™ would be statistically significantly more effective than the Sham control, with strength of evidence meeting the standard requirement of a 0.0125 one-sided false positive error rate (incorporating an adjustment for multiplicity arising from comparing each dose with the Sham control).

The operating characteristics for this three-category decision guideline are:

1. The false-positive error rate of the screening procedure is low. In particular, if a given dose of Zimura™ truly provides no improvement in the rate of GA growth over 12 months, then there is only a 10% chance of bringing that dose forward to a Phase 3 trial and only a 1.25% chance of reaching the false positive conclusion that that dose regimen provides a statistically significant improvement in efficacy relative to a Sham control. Given that there will be two pairwise comparisons, if both doses of Zimura™ truly provide no improvement in the rate of GA growth over 12 months, then the probability of achieving a false positive conclusion for further study for at least one dose regimen likely would be in the range of 15% to 17% (when one takes into account the positive correlation between these two

assessments), and the probability of reaching a conclusion that at least one dose regimen provides a statistically significant improvement in efficacy relative to a Sham control is only 2.5%.

2. The false-negative error rate is low. If a given dose of Zimura™ truly provides a 28% reduction in the rate of GA growth over 12 months, then there is only a 10% chance that that dose of Zimura™ would be discarded, and thus a 90% chance that it would be evaluated in a subsequent confirmatory Phase 3 trial. Given that there will be two pairwise comparisons, if both doses of Zimura™ truly provide a 28% reduction in the rate of GA growth over 12 months, then it is likely (when one takes into account the positive correlation between these two assessments) that there is at least a 95% chance that at least one dose would be evaluated in a subsequent confirmatory Phase 3 trial. If a given dose of Zimura™ truly provides a 28% reduction in the rate of GA growth over 12 months, there is a 63% chance that that regimen will have a statistically significant improvement in efficacy (at one-sided  $p < 0.0125$ ) relative to the Sham control.

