### **11.6.2 Significance Levels**

The overall (one-sided) false positive error rate in this trial, accounting for the conduct of two pairwise comparisons with Sham control, is 0.025 for the analysis of the primary endpoint.

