### 3.2.1 Intention-To-Treat (ITT) Population

The intention-to-treat population (ITT) will consist of all randomized subjects who received at least one dose of study drug, irrespective of the dose actually received. Subjects will be analyzed in the treatment group assigned at randomization. Subjects will be included in a particular analysis, for a particular population, if relevant data is available for analysis (e.g., the primary analysis will require both Baseline and at least one post-Baseline GA measurement, to calculate a change score).

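### The stated 15% to 17% chance of wrongly advancing at least one ineffective dose is slightly too low: the printed design gives about 17.7%

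*Protocol*

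**What the plan says.** Protocol 11.3 describes a three-category guideline for each dose, according to whether the estimated reduction in the 12-month GA growth rate "is less than 14%, is from 14% up to 24.5%, or is at least 24.5"%. For a dose with no effect, "there is only a 10% chance of bringing that dose forward to a Phase 3 trial". The stricter criterion, a statistically significant benefit, carries for such a dose "only a 1.25% chance of reaching the false positive conclusion". For two ineffective doses, the chance that at least one is taken forward "likely would be in the range of 15% to 17"%; the protocol attributes this to the positive correlation between the two comparisons.

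The section also gives the analysis counts. The 2 mg comparison combines 26 v 26 subjects from Part 1 with 40 v 80 from Part 2, stratified by Part. The 4 mg comparison "will be based on the 80 subjects randomized to each of these two arms in Part 2".

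**The concern.** The joint false-go probability for two comparisons is fixed by the per-dose rate and the correlation between the two estimates. Protocol 11.3 states the first and prints the counts that determine the second, so the 15% to 17% range can be checked directly. The unknown standard deviation cancels out of the correlation.

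The two comparisons have less in common than in an ordinary three-arm trial with one control. The 2 mg estimate takes about a third of its weight from Part 1, which contributes nothing to the 4 mg estimate. The 2 mg arm in Part 2 is also half the size of the Sham arm. Both features lower the correlation and so raise the chance that at least one dose is advanced by mistake. That chance is a stated operating characteristic of the Phase 3 decision, and the printed figure errs on the favourable side.

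**Working it through.** **Reproducing the single-dose figures.** With a normal approximation, the cut-offs and error rates imply a standard error of 14/1.2816 = 10.92 percentage points, or 24.5/2.2414 = 10.93. At a true 28% reduction:

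- chance of advancing: Φ((28 − 14)/10.92) = 90.0% (stated 90%);
- chance of significance: Φ((28 − 24.5)/10.93) = 62.6% (stated 63%).

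The sponsor's single-dose method is therefore recovered.

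**Correlation of the two comparisons** (variances in units of σ², counts from Protocol 11.3):

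- 2 mg, Part 1 information: 1/(1/26 + 1/26) = 13.00.
- 2 mg, Part 2 information: 1/(1/40 + 1/80) = 26.67.
- Total: 39.67. Part 2 weight: 26.67/39.67 = 0.672. Variance: 1/39.67 = 0.02521.
- 4 mg variance: 1/80 + 1/80 = 0.0250.
- Covariance, from the 80 shared Part 2 Sham subjects: 0.672/80 = 0.00840.
- Correlation: 0.00840/√(0.02521 × 0.0250) = 0.335.

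**Chance that at least one ineffective dose is advanced.** This is 0.10 + 0.10 − P(both estimates exceed z = 1.2816), using a bivariate normal with that correlation. At 0.335 the joint term is 0.0233, so the result is 0.20 − 0.0233 = 0.1767, or 17.7%. A simulation of 2 million draws gives 17.6%. Applying one common 14% cut-off with the slightly unequal standard errors also gives 17.7%.

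**Other ways of forming the 2 mg comparison, and reference values:**

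| Case | Correlation | At least one false advance |
|---|---|---|
| Stratified by Part (as Protocol 11.3 states) | 0.335 | 17.7% |
| Parts pooled, 66 v 106 | 0.381 | 17.4% |
| Part 2 only, 40 v 80 | 0.408 | 17.3% |
| Independent comparisons | 0 | 19.0% |
| Three equal arms, one shared control | 0.5 | 16.8% |
| Needed for 17% | 0.46 | 17.0% |
| Needed for 15% | 0.74 | 15.0% |

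The pooled correlation is (1/106)/√((1/66 + 1/106) × 0.0250) = 0.381. Every value obtainable from the printed counts lies above 17%. The equal-arm case falls inside the stated range, but it is not this design.

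**The other joint figures.** At a correlation of 0.335, at least one dose advances with probability 1 − 0.0233 = 97.7% when both truly give 28%, which agrees with the stated minimum of 95%. At least one ineffective dose is significant with probability 2.4% when each is tested at 0.0125, which agrees with the stated 2.5%.

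**The case against.** The strongest reply is that the gap is close to rounding and depends on the model. The protocol hedges the figure, gives enrolment as approximate, and says that the categories are not strict decision rules. Moreover, SAP 7.2 enters Part only as a main effect, and the stratification factors it crosses with visit are listed in SAP 2.3 without Part. If Baseline, Month 6 and Month 12 are all modelled as responses, a Part term that is constant over visits does not adjust the growth contrast. The correlation is then 0.381 and the figure 17.4%, which rounds to 17%. This stands as a limit on precision: 17.4% to 17.7% is defensible, and 17.7% belongs to the stratified analysis that Protocol 11.3 describes. It does not rescue the range, because 17.4% is still above 17% and nothing in the counts comes near 15%.

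A reader might go further and infer that the 90% and 63% powers are overstated because no allowance for missing FAF is visible. The documents do not support that. Protocol 11.3 takes its precision from another trial's results, which may already reflect dropout there, and parts of the section are redacted. Nor is a subject without Month 12 data wholly lost: SAP 3.2.1 says that "the primary analysis will require both Baseline and at least one post-Baseline GA measurement", and the repeated-measures model retains Month 6.

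**Conclusion.** The 15% to 17% range does not follow from the design printed in the same section. The figure is about 17.7% for the analysis stratified by Part and 17.4% if the Parts are pooled, an overshoot of 0.4 to 0.7 percentage points above the top of the range. The lower end is unreachable, since it needs more than twice the correlation of the stratified analysis. The result assumes approximately normal estimates, equal variance across arms and Parts, the printed counts, and exactly 10% per dose.

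This is a minor error in a reported operating characteristic. A reader might infer that control of the significance error is also affected, but it is not: the overall one-sided rate, which under Protocol 11.6.2 "is 0.025 for the analysis of the primary endpoint", is respected. The 1.25%, 2.5%, 90%, 63% and at-least-95% figures stand as stated.

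**What to change.** In Protocol 11.3, replace 15% to 17% with about 17.5% to 18%, and state that the value is 17.7% for the analysis stratified by Part. A short note of the correlation used (about 0.33, from the shared Part 2 Sham arm) would let a reader verify it. If the fitted 2 mg model does not adjust the growth contrast for Part, the note should give 17.4% instead. The cost is one edited sentence with a slightly less favourable number. The cut-offs, alpha and sample size need no change.
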